#### I. DEFININTIONS AND ADVERSE EVENT REPORTING

Adverse Device Effect - Adverse Device Effects are adverse events that are device related. Adverse Device Effects can be classified as either Serious or Unanticipated.

Adverse Event - any untoward medical occurrence in a subject (does not imply that there is a relationship between the adverse event and the device under investigation) [equivalent to an observation]

Serious Adverse Event (SAE) - adverse event that a) led to a death, b) led to a serious deterioration in the health of the subject that

- Resulted in a life-threatening illness or injury,
- Resulted in a permanent impairment of a body structure or a body function,
- Required hospitalization or prolongation of existing hospitalization,
- Resulted in medical or surgical intervention to prevent permanent impairment to body structure or a body function [equivalent to a complication]

SAEs must be reported via eCRF (electronic case report form) immediately but no later than 3 calendar days upon site awareness.

Subject - is a patient who meets the inclusion and exclusion criteria that elects to enroll in the study and provides informed consent

Unanticipated Device Adverse Event (UDAE) – serious adverse device effect which, by its nature, incidence, severity or outcome has not been identified in the current version of the risk analysis report..

UADEs must be reported to MedPass International by telephone and/or email within 24 hours upon site awareness.

# II. BACKGROUND SIGNIFICANCE

# Mitral Regurgitation, Transapical mitral valve repair, and the TSD-5

Mitral valve disease is the most common valvular heart disorderi, with nearly 4 million Americans estimated to have severe mitral valve regurgitation ("MR"). MR results in a volume overload on the left ventricle which in turn leads to ventricular dilation, decreased ejection performance, pulmonary hypertension, symptomatic congestive heart failure, atrial fibrillation, right ventricular dysfunction and death. Successful surgical mitral valve repair restores mitral valve competence, abolishes the volume overload on the left ventricle, improves symptom status and prevents adverse left ventricular remodeling.

The large majority of mitral regurgitation results from either **degenerative disease** (caused by elongated or ruptured native chords that fail to support the mitral valve leaflets) or **functional** ischemic or idiopathic MR (the motion of the normal mitral valve leaflets is restricted by the enlarged ventricle) both of which lead to ineffective valve closure and regurgitation.

At present 2/3rds of mitral valve procedures in North America are performed on subjects with degenerative MR and the case mix is estimated to be similar in the European Union. A common method of treating degenerative mitral valve regurgitation during open cardiac surgery involves replacing and/or supplementing elongated or ruptured chords with artificial chords made of ePTFE. While open cardiac surgery has a low mortality risk, it results in substantial disability and has important risks, including stroke, bleeding, infection, and

Page 3 of 15

replacement rather than repair of the mitral valve. The ability to place ePTFE artificial cords on the mitral valve without a chest-splitting incision, cardiopulmonary bypass, or stopping the heart would represent a tremendous advance in decreasing the risk and invasiveness of mitral valve repair.

While considerable efforts have been directed toward minimally invasive chordal replacement, the only commercially available option available in the EU is a device from NeoChord Inc. The chordae replacement surgical procedure is performed using the NeoChord DS1000 device. The procedure is performed on a beating heart through a 2 to 3 inch incision between the ribs. Echocardiographic guidance is used during the procedure to aid the surgeon in positioning the device on the mitral valve leaflets. The device enters the heart through the apex, extends into the left ventricle and between the mitral valve leaflets. When the echocardiographic guidance confirms the proper position on the valve leaflets, the ePTFE suture is deployed and attached to the leaflet. The suture is then pulled through the apex of the heart as the DS1000 is removed. The correct length of the suture is determined using the echocardiographic guidance and observing the improvement in the mitral valve regurgitation in the beating heart.

Although this technology presents a minimally invasive solution for the replacement of chordae tendineae, the device requires the surgeon to enter the left ventricle with a large shaft (~10mm) for every suture. Additionally, the device limits suture placement to the free edge of the mitral leaflet and requires the operator to grasp the free edge of the moving mitral leaflet. Neochord has reported several instances of ePTFE suture tear-outs from the mitral valve leaflet. There is a need for a less invasive, beating heart cordal delivery device with more a more effective anchoring mechanism.

To address this unmet need, Harpoon Medical has developed a novel small-diameter (<3mm) rigid linear device with a needle wrapped with ePTFE in a preformed knot configuration The device may be delivered via a purpose-designed valved introducer inserted a few centimeters "off apex" just below the papillary muscle to secure cords to the mitral leaflet with a "bulky knot" anchor or directly into the left ventricle using an entry point a similar entry point. This knot is housed inside the rigid metal shaft (<3mm) of the delivery device until proper positioning is achieved on the ventricular side of the mitral leaflet with transesophageal echocardiography (TEE). To deploy and form the knot on the atrial side, a handle mechanism is actuated which advances the needle and knot through the leaflet, withdraws the needle out of the knot, then pulls the ends of the suture to form/expand the bulky knot on the atrial side of the leaflet. The ends of the suture are then released from the delivery system which can then be withdrawn from the patient leaving the bulky knot in place. The process can be repeated with additional devices to deliver additional sutures in the prolapsed leaflet. The length of the ePTFE cords sutures can be adjusted in real-time under echo guidance to optimize the surface of coaptation between leaflets before they are secured to an ePTFE pledget on the epicardium.

The Harpoon device will provide many significant advantages over current surgical interventions including: 1) a small minimally invasive incision, 2) no sternotomy, 3) no cardiopulmonary bypass, 4) no aortic manipulation, 5) a direct path to the valve plane, 6) performed on a beating heart, 7) real-time TEE-guided chordal length adjustment and 8) less complicated procedure that is teachable and adoptable. The only intracardiac implant is an

Version: HMFIM -1000-PL-04, 07 August 2019 Page 4 of 15

ePTFE suture which has a 25+ year history of safety in conventional mitral valve repair procedures.

Importantly, the Harpoon approach will not compromise subsequent traditional open-heart mitral valve repair or replacement procedures. Collectively, these benefits should translate into dramatically less pain and disability, lower hospital lengths of stay, fewer strokes, less renal failure, fewer wound infections and lower peri-procedural mortality.

Currently, mitral valve surgical procedures require a 3 to 6 hour procedure with 4 to 7 days of in hospital recovery (including at least a 1 day in the ICU) and a month or more of recovery before the subject can return to work. With the Harpoon device, the procedure will be transformed in to a 45 to 60 minute procedure where the subject can be discharged within 24 hours and can return to work within a week.

Treatments: At this time, there are treatments available to replace ruptured or elongated cords and result in the reduction of MR; however there is no currently effective medical therapy that treats or cures MR. The current technologies available to address the structural defects of mitral regurgitation include:

- Open heart operations to repair or replace the mitral valve. Open cardiac mitral valve operations require either a sternotomy or a thoracotomy, cardiopulmonary bypass, aortic manipulation and cardioplegic cardiac arrest. Mitral valve repair is carried out with leaflet resectional techniques (Carpentier) or nonresectional techniques using ePTFE cords placed under direct vision. Because the heart is flaccid and arrested, sizing the cords is difficult. Improper sizing of the cords may result in a failed or ineffective mitral valve repair. The success of mitral valve repair is significantly dependent on the expertise of the operating surgeon. For patients with degenerative mitral valve disease, mitral valve replacement is inferior to mitral valve repair (short-term higher perioperative mortality and long term substantially higher risks of stroke and prosthetic valve endocarditis as well as either the need for lifelong anticoagulation (mechanical valve) or the risk of repeat mitral operation (bioprosthetic valve). Mitral valve replacement (compared to repair) is a risk of open cardiac surgery. This procedure is also very invasive and not a feasible option for all patients.
- In 2008, Evalve received CE mark to market the MitraClip in the EU. Shortly thereafter,
  the company was acquired by Abbott Labs. The implantation of MitraClip does not involve
  open-heart surgery, but mimics the surgical method of edge-to-edge valve repair where
  the mitral valve leaflets are clipped together with the device instead of being sutured
  together. Extensive clinical experience with the MitraClip has been collected over the last
  six years and the clinical efficacy has been mixed.
- In 2013, Neochord released a CE marked, Class III medical device to the EU as a minimally invasive procedure that is performed on a beating heart to replace cords that have become elongated or ruptured. Neochord does not involve open-heart surgery, but mimics the surgical method of suturing the free-edge of the mitral valve to install replacement cords. The surgical entry point is through the apex of the heart for the deployment of a suture by the Neochord device. Initial clinical results have been promising but when the cordal suture is not properly anchored the procedure does not produce a reliable repair.

Version: HMFIM -1000-PL-04, 07 August 2019 Page 5 of 15

Although these procedures are available to a cardiothoracic surgeon in the EU, there is still a need for additional minimally invasive treatment options for patients suffering from mitral valve regurgitation. The MitraClip is limited to an edge-to-edge repair which is rarely used in isolation during open heart operations and has demonstrated mixed clinical efficacy. The large shaft of the NeoChord device creates significant trauma to the left ventricle and the device design limits the placement of the cordal suture to the free edge of the mitral valve leaflet which has impacted the durability of the repair. It is expected that the Harpoon Medical transapical suturing device will be a valuable treatment alternative for patients suffering from mitral valve regurgitation because it can access the left ventricle like the NeoChord device but with a smaller shaft or via a small valved introducer and has a more securing anchoring mechanism that can be deployed anywhere on the mitral valve leaflet.

# III. STUDY OBJECTIVES

The purpose of this study is to evaluate the safety and performance of the Harpoon Medical TSD-5. The data collected from this trial was used to support the design of the study to support CE Mark of the TSD-5 Device. The Harpoon Medical device received CE Mark in December of 2017. Enrollment in this trial was completed as of November 2017. Follow-ups range from 12 to 36 months. The purpose of this amendment is to increase the frequency of follow-up and to extend the follow-up to 5 years post-implant.

# **Performance Goals**:

**Primary Performance Endpoints**: To demonstrate that the TSD-5 performs as designed and has the ability to successfully implant one or more ePTFE cords on the mitral valve via a small left thoracotomy on the beating heart and reduce mitral regurgitation from severe to </= moderate at the conclusion of the procedure and at 30 days post-procedure.

**Secondary Performance Endpoints:** Severity of mitral regurgitation at 6 months, 12 months, 18 months, 24 months, 30 months, and 36 months follow-up shall be tracked and recorded.

#### Safety Goals:

**Primary Safety Endpoints**: Procedure freedom from Serious Adverse Events (SAEs) during the ePTFE implantation procedure, at discharge, and at 30 days follow-up shall be tracked and recorded.

**Secondary Safety Endpoints** Freedom from Serious Adverse Events (SAEs) at 6 months, 12 months, 18 months, 24 months, 30 months, and 36 months follow-up shall be tracked and recorded.

# IV. SUBJECT SELECTION

Subjects will be screened, selected, and enrolled in this trial based on the inclusion and exclusion criteria. Once enrollment has occurred, performance of the Harpoon transapical mitral repair procedure will occur within 30 days.

## **Intended Use:**

The TSD-5 is intended to secure ePTFE sutures on the mitral valve for the treatment of mitral valve disease.

#### **Inclusion Criteria:**

- All subjects referred for mitral valve surgery
- Presence of severe mitral regurgitation as read on an echocardiographic study performed within 60 days prior to procedure. Assessment of mitral regurgitation will be performed by the investigational site echocardiography laboratory and confirmed by the Core Echocardiography Laboratory using an integrative method.
- Age > 18 years
- Estimated post-ePTFE cordal implantation coaptation surface is adequate in the judgment of the operating surgeon and the patient eligibility committee
- Degenerative mitral valve disease
- Subject is able to sign informed consent and able to return for follow-up and is capable of participating in all testing associated with this clinical investigation
- Women of child-bearing potential have a negative pregnancy test
- Able to sign informed consent

# **Exclusion Criteria:**

- Age < 18 years

- · Infective endocarditis
- Anterior or bileaflet prolapse
- Functional mitral regurgitation
- History of Mediastinal Radiation
- Inflammatory (rheumatic) valve disease
- Requirement for concomitant cardiac surgery (e.g., coronary artery bypass grafting (CABG), aortic valve surgery, etc.)
- Symptomatic coronary artery disease
- Cardiogenic shock at the time of enrollment
- ST segment elevation myocardial infarction requiring intervention within 30 days prior to enrollment
- Evidence of cirrhosis or hepatic synthetic failure
- Pregnancy at the time of enrollment (women of child bearing age should have negative pregnancy within 14 days of surgery)
- Severe pulmonary hypertension (PA systolic pressure > 70 mmHg)
- Previous cardiac surgery, or surgery on the left pleural space
- Left ventricular, atrial or appendage thrombus
- · Severely calcified mitral leaflets
- Recent stroke (< 6 months) with permanent impairment
- EuroScore (for mitral valve repair) > 8%
- Subjects with contraindications to transesophageal echocardiography
- Severe left or right ventricular dysfunction
- NYHA Class IV
- Renal insufficiency CKD stage 3b or worse (GFR < 45 ml/min/1.73 m^2)
- Patient is participating in another clinical study for which follow-up is currently ongoing. (Co-enrollment in an investigational device or interventional study)
- Patient with non-cardiac co-morbidities and life expectancy < 1 year

• Patient has a condition or conditions that, in the opinion of the Investigator, preclude participation, including willingness to comply with all follow-up procedures

### V. SUBJECT ENROLLMENT

This is a prospective, nonrandomized, single-centered European study designed single arm study to demonstrate the performance and safety of the Harpoon Medical TSD-5 in Subjects with degenerative mitral regurgitation. A maximum of fifty (50) subjects will be enrolled. The estimated enrollment period is 24 months, and all subjects shall be followed for 30 days, 6 months, 12 months, 18 months, 24 months, 30 months, 36 months, 48 months and 60 months after ePTFE implantation in accordance with the Schedule of Clinical Investigations (see below).

Subject withdrawal from the study: A withdrawal refers to a Subject who is determined to be inactive in the study due to physician discretion, Subject choice (withdrawal of consent), and loss to follow-up or Subject death. Final status will be reported on all Subjects as per the informed consent. Three documented phone calls and a registered/certified letter will be used to assure that there is minimal loss to follow-up. If these efforts to contact the Subject are unsuccessful, the Subject will be considered lost to follow-up.

Pre-procedure/baseline evaluations: All Subjects enrolled in the study will undergo transthoracic echocardiography and transesophageal echocardiography prior to surgery. These are routine preoperative studies for Subjects undergoing heart valve surgery.

Physical Assessment: All study Subjects will undergo a comprehensive history and physical examination. Once enrolled, a physical assessment must be completed within 30 days of the procedure and recorded on a Case Report Form (CRF). In addition to a physical examination and a comprehensive history, the physical assessment will include:

- Vital signs, 12-lead ECG, Laboratory assessment (including WBC count; Hemoglobin; hematocrit; platelet count; creatinine Level, Total Albumin, Total Bilirubin; INR; BNP, NTproBNP) and a chest radiograph (X-Ray)
- A serum pregnancy test for females with childbearing potential (age < 50 years) will be completed within 14 days prior to the procedure.
- As per the standard of care for valve surgery, any subject with symptoms of coronary artery disease and all subjects age >/= 45 years without risk factors shall undergo preoperative diagnostic left heart catheterization ("LHC").
- · Pulmonary Function Tests, when clinically indicated
- 6 Minute Walk test

Standard transthoracic echocardiographic evaluation: Standard transthoracic echocardiographic assessment of the degree of mitral regurgitation will be performed as described in "Recommendations for evaluation of the severity of native valvular regurgitation with two-dimensional and Doppler echocardiography" (Zoghbi et al, J Am Soc Echocardiography 2003; 16:777-802)

An integrative approach will be used, and Subjects will be categorized as having one of:

- 1. None/trivial
- 2. Mild

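### The lost-to-follow-up rule has no vital-status check, so a death unknown to the site can be recorded as a loss and not as a fatal SAE

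*Combined protocol and SAP*

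**What the plan says.** Section V (Subject Enrollment) describes the tracing effort: "Three documented phone calls and a registered/certified letter will be used to assure that there is minimal loss to follow-up". It then assigns a status: "If these efforts to contact the Subject are unsuccessful, the Subject will be considered lost to follow-up". The same paragraph lists death apart from loss among the reasons for withdrawal ("Subject choice (withdrawal of consent), and loss to follow-up or Subject death") and promises that "Final status will be reported on all Subjects as per the informed consent". It does not say how that status is to be established.

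Section I counts as serious any "adverse event that a) led to a death", and the site must report SAEs "immediately but no later than 3 calendar days upon site awareness". The secondary safety endpoint in Section III is "Freedom from Serious Adverse Events (SAEs) at 6 months" and at further visits, the last at 36 months. Under Section X and the Clinical Endpoint Committee text, the committee adjudicates SAEs through the 36-month visit. Follow-up itself runs to 60 months. Section VII plans descriptive reporting only and gives no rule for subjects who are lost.

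**The concern.** Death is both the gravest SAE and an obvious reason why a subject stops answering. A rule that turns silence into a loss, without asking whether the subject is alive, can move exactly these events out of the safety count. The study has at most 50 subjects and no hypothesis test, so the reported proportions are its result, and a single event is visible in them.

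The rest of the plan offers no dependable second route to such a death. SAE reporting starts when the site becomes aware. The committee sees what has been reported or identified. The retrospective collection described after Appendix A depends on the subject having returned to hospital and on the patient's own signature.

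**Working it through.** **Inputs.** From the documents: N = 50, the maximum enrolment in Section V, and a safety endpoint that ends at 36 months. The documents give no mortality, SAE rate or loss rate, and Section VII says that no formal sample size was calculated, so there is no planned figure to reproduce.

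Assumptions, for illustration only: K = 5 or 10 subjects with a known SAE; L = 1 or 5 subjects lost, none with an earlier SAE; m of the lost have in fact died, and the other lost subjects are event-free.

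**Step 1: effect of one missed death, with everything else unchanged.**

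- *Lost subjects counted as event-free.* Reported (N − K)/N, corrected (N − K − m)/N, difference m/N. With K = 5 and m = 1: 45/50 = 90.0% against 44/50 = 88.0%, which is 2.0 points per death.
- *Lost subjects dropped.* Reported (N − K − L)/(N − L). Once one death is found, that subject returns to the denominator as a failure: (N − K − L)/(N − L + 1). With K = 10 and L = 5: 35/45 = 77.8% against 35/46 = 76.1%, a difference of 1.7 points. With K = 5 and L = 1: 44/49 = 89.8% against 44/50 = 88.0%, a difference of 1.8 points.
- *Lost subjects censored in a time-to-event estimate.* The missed death is a downward step that is left out, so the direction is the same.

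Under all three treatments the missed death itself raises reported freedom from SAE. If the subject had an earlier SAE, the endpoint does not change.

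**Step 2: net error against full knowledge of all 50.** The true value is (N − K − m)/N. It differs from Step 1 when lost subjects are dropped, because the living, event-free lost subjects are then dropped as well.

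| K | L | m | Dropped | Counted event-free | True | Error, dropped | Error, event-free |
|---|---|---|---|---|---|---|---|
| 5 | 1 | 1 | 89.8% | 90.0% | 88.0% | +1.8 | +2.0 |
| 5 | 5 | 5 | 88.9% | 90.0% | 80.0% | +8.9 | +10.0 |
| 10 | 5 | 1 | 77.8% | 80.0% | 78.0% | −0.2 | +2.0 |
| 10 | 5 | 5 | 77.8% | 80.0% | 70.0% | +7.8 | +10.0 |

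The third row shows that overstatement on balance is not assured if lost subjects are dropped.

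**Step 3: how likely is any such death?** With 5 lost and an assumed death risk p for each, the chance of at least one death among them is 1 − (1 − p)^5. For p = 2%, 5%, 10% and 20% this gives 9.6%, 22.6%, 41.0% and 67.2%. The documents do not say where in this range, or outside it, the trial lies.

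**The case against.** The strongest reply is that the text never says that a dead subject is filed as lost. Death is its own category, final status is promised for everyone, and a call or letter to the home may well reach a relative. This is right as far as it goes: misclassification is possible, not certain. It does not close the gap, because no source for final status is named and a loss is itself a status that can be reported.

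Permission for wider tracing may also exist already. Appendix A schedules a Release of Medical Information at screening, and Section V ties final status to the informed consent. The scope of neither can be judged from the public text, so the absence of permission should not be assumed. The documents do show that the tracing rule does not call on any such permission.

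A reader might infer that the main harm lies in the extension to 48 and 60 months, or that 60-month survival will be overstated by several points. The documents do not support this. The SAE-freedom endpoint and the committee's stated scope both end at 36 months, and the plan names no survival endpoint, no 60-month SAE endpoint and no censored estimator. It is also unclear whether the loss rule applies to subjects who had completed the 36-month schedule and are approached again under Version 04.

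Finally, this is a small descriptive study with registry-style late follow-up. That limits the weight of the point but does not remove it.

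**Conclusion.** The concern holds in a limited form. As written, Section V lets a death unknown to the site be recorded as a loss without any check of vital status, and no other provision reliably finds it.

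Through 36 months, each such death in a subject without an earlier SAE overstates freedom from SAE by about 2 points: 2.0 if all 50 are counted, and 1.7 to 1.8 in the worked cases where lost subjects are dropped. Fifty is a maximum. Section VI follows converted subjects for only 30 days and exits reoperated ones after 30 days, so if those subjects leave the denominator, each death weighs somewhat more.

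The number of such deaths is unknown, and the net error depends on a treatment of lost subjects that Section VII does not fix. A general statement that late safety is overstated would therefore go too far. After 36 months the point concerns only whether final status and deaths are reported accurately.

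**What to change.** In Section V, after the calls and letter, require that vital status be sought before a subject is classed as lost. If the subject has died, the date and cause of death should be sought too. Sources would be the treating physician, next of kin, hospital record or civil registry, as the existing consent, the Release of Medical Information and local law permit. A death found this way is reported as an SAE with its date. Otherwise the date last known alive is recorded.

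If existing permission does not cover this, add a line to the Version 04 consent letters, which subjects must sign anyway. Such a line cannot cover subjects who died before signing; where nothing else permits the check, their status is reported as unknown.

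In Section VII, add the numbers alive, dead and of unknown status at 36 and 60 months, and state how lost subjects enter the denominator for freedom from SAE.

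The cost is a few record queries, possibly a privacy permission, and a safety figure that may turn out slightly less favourable.
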